**Table 1. Proposed Outcomes for the Pre-diabetes and Diabetes Cohorts**

Outcomes	Definition	Notes
Pre-diabetes cohort		
Weight loss during counseling	Weight lost from first IBT visit to final IBT visit	Available at all PaTH sites
Weight loss maintenance	% of weight lost during program and maintained over remaining time period, reported by year	Available at all PaTH sites
Diabetes incidence	% of patients who develop diabetes per year following weight counseling	Available at all PaTH sites
Patient-reported outcomes	-SF-12 -PHQ-2, PHQ-8, PHQ-9 -Physical function -sleep -fruit and vegetable consumption -social support -physical activity -PROMIS (PROMIS 29, physical function, depression) -healthy lifestyles -patient reported medication reconciliation	Available at some sites – Formal inventory of PROs will be collected at each institution at the beginning of the project, to be included as secondary outcomes
Diabetes cohort		
Weight loss during counseling	Weight lost from first IBT visit to final IBT visit	Available at all PaTH sites
Weight loss maintenance	% of weight lost during program and maintained over remaining time period, reported by year	Available at all PaTH sites
Patient reported outcomes	-SF-12 -PHQ-2, PHQ-8, PHQ-9 -Physical function -sleep -fruit and vegetable consumption -social support -physical activity -PROMIS (PROMIS 29, physical function, depression) -healthy lifestyles -patient reported medication reconciliation	Available at some sites – Formal inventory of PROs will be collected at each institution at the beginning of the project, to be included as secondary outcomes
Uncontrolled diabetes	Average A1c > 9 or no A1c	Available at all PaTH sites
Controlled blood pressure	SBP < 140, DBP < 90, averaged across values over year	Available at all PaTH sites
On a statin medication	Evidence of a statin medication on current EHR medication list	Available at all PaTH sites
Receiving annual eye exam	Documentation of eye exam once in past year	Available at all PaTH sites
Receiving annual urinary microalbumin test	Documentation of lab testing for urinary microalbumin at least once in past year	Available at all PaTH sites
Lower extremity amputations	Documentation of procedure for lower extremity amputation or billing code through health plans in past year	Available at all PaTH sites
Diabetes Service Use	-Clinic visit with primary or secondary diagnosis of diabetes -Emergency department visit with primary or secondary diagnosis of diabetes -Hospitalization with primary or secondary diagnosis of diabetes	Available at all PaTH sites
Exposure variables		
Individual level	-Sociodemographics (e.g., age, sex, race, insurance status, rural vs. urban) -Medical co-morbidities	Available at all PaTH sites
Provider/practice level	-Practitioner type (advanced practice vs. MD/DO) -Practitioner specialty -Practice size (# of providers) -Practice type (multispecialty, academic) -Practice setting (rural vs. urban)	To be determined

**Data Transfer.** The PaTH network has established an operational data infrastructure with the necessary technical safeguards as agreed upon in the PaTH Data Use Agreement (DUA) for sharing and analyzing data while addressing data confidentiality and security concerns. PaTH has deployed two mechanisms for storing, protecting, and sharing data (as described previously under PaTH Governance and Regulatory Issues): (1) data with PHI are stored and protected behind each institution's firewall in the distributed data network and (2) de-identified data are sent to the PaTH data center at

the University of Pittsburgh (CERC-DC). Once data integration is accomplished at each site, sites will remove all PHI and send the de-identified version of the integrated data to the CERC-DC through PaTH's virtual private network/secure file transfer protocol (VPN) which has been operational for data transmission since November 2014. Data analysis can then be performed via secure remote computing using standard statistical software packages (e.g., SAS). This model ensures that the highest level of privacy and confidentiality for the data that are maintained at each site, the CERC-DC, and at Penn State.

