**Aim 2: Compare patient weight loss and diabetes-related outcomes among those who receive obesity screening and counseling to those who do not, following implementation of preventive service coverage.** We will examine post-policy impact of obesity screening and counseling in a cohort of patients with diabetes and at high risk for diabetes. Specific outcomes to be examined include weight loss, diabetes incidence, and diabetes outcomes (including hemoglobin A1c, controlled blood pressure, use of a statin medication). Further, we will determine patient characteristics, including demographics (age, race/ethnicity, rurality), and practice characteristics, including provider type, and their impact on receiving/providing obesity screening and counseling. Understanding patient and practice characteristics most likely to engage in obesity counseling can identify best practices and inform how to increase engagement by both patients and providers.

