### **3.2 Exclusion Criteria**

- Patients under the age of 18

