***At-risk Cohort Definition.*** The cohort of patients under study will be defined as patients age 18 and older who are at risk for the development of diabetes, based on being overweight. Patients seen at one of the four PaTH institutions will be included in the at-risk cohort if they have a  $BMI \geq 25 \text{ kg/m}^2$ , based on most recent recorded weight and at least one recorded height. The at-risk cohort will be further limited to patients who will likely to be captured in the PaTH EHR records or claims data so that outcome assessments can occur. Thus, we will further limit the at-risk cohort to patients who have either: (1) had at least 2 outpatient primary care visits in one of the PaTH health systems in the past 3 years (since January 1, 2012), or (2) for whom claims data is available. The cohort will be dynamic, with new patients added into the cohort after 2015 as they meet the at-risk cohort definition prospectively. Patients will not be removed from the cohort, even if they are no longer overweight. The observational period for the outcome variables will be for the 10-year period from 2009-2019, thus including 3 years of data prior to the first policy change (CMS instituting coverage for intensive behavioral therapy for obesity) and 3 years after the last policy change (Pennsylvania Medicaid expansion) under study.

[figure not shown]
intensive behavioral therapy for obesity) and 3 years after the last policy change (Pennsylvania Medicaid expansion) under study.

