To evaluate the impact of policy changes on these outcomes, we will examine how these outcomes change over time, in response to the policy changes. As descriptive analyses, we will plot the mean trajectory of each yearly outcome at clinic level, health system level and state level. The statistical modeling of patterns of changes in individual level outcomes will be carried out through multi-level mixed-effects models. The mixed-effects model is a common and popular modeling technique for longitudinal data. A mixed-effects model can accommodate within- and between-subjects variability, as well as serial correlations. In addition, it has the flexibility to incorporate time-dependent covariates, incomplete data, and heteroscedasticity of the variances and correlations. The mixed-effects model will be specified in a multi-level fashion so that different levels of variability (e.g., individual characteristics, social environment, built environment) can be taken into account. The pattern of changes in the outcome will be assessed for pre- and post-periods, respectively, based on the piecewise/segmented regression models. The slope of each segment indicates the trend of change in diabetes outcome in that period. Therefore, the change in the trend/slope post-policy implementation may reveal the actual impact of the new policy controlling for baseline level and trend. Such modeling strategies share the same spirit of interrupted time series analysis. While the classical interrupted time series design often generates a single long series of data, we have a large number of short series from each individual subject, namely, longitudinal data. Depending on the types of the outcomes, we will specify mixed-effects models based on logistic

regression for a binary outcome, Poisson regression for a count outcome and linear regression for a continuous outcome as detailed below.

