where  $\mathbf{x}_{mijk}$  is the vector of regressors for the fixed effects,  $\boldsymbol{\beta}_m$  is the corresponding vector of fixed-effects parameter coefficients,  $\mathbf{z}_{ij}$  is a vector of cluster-level regressors for the random effects for the  $j^{\text{th}}$  cluster of the  $i^{\text{th}}$  state,  $\boldsymbol{\gamma}_{1ij}$  is the cluster-level random-effect coefficients and is common to all  $m$ , and  $\boldsymbol{\gamma}_{2mijk}$  is the subject-level random-effect coefficients associated with the parameter  $\beta_m$  for the  $k^{\text{th}}$  subject within the  $j^{\text{th}}$  cluster. The random effects are assumed to follow a multivariate normal distribution with mean zero. Because the vector  $\mathbf{x}_{mijk}$  may include subject-level, cluster-level and state-level exposure variables, the fixed effects parameter vectors  $\boldsymbol{\beta}_1$  and  $\boldsymbol{\beta}_2$  represent the effects of different exposure variables on the annual changes in the pre- and post-periods. Thus, we may perform statistical tests to examine whether there are differences in trends between the pre- and post-periods overall and for each state, and whether the patterns of changes differ between the states.

Similarly for a count outcome  $Y_{ijkt}$  (e.g., number of clinical visits), we define the expected value  $\mu_{ijkt} = E(Y_{ijkt})$  and apply a Poisson regression model based on the natural log link function. The log expected number of clinical visits,  $\log(\mu_{ijkt})$ , can be modeled with the aforementioned segmented mixed-effects model. The use of an offset term in the models yields the estimates of the rate of clinical visits rather than the mean number of visits. The fixed-effect parameters,  $\beta_1$  and  $\beta_2$ , represent the effects of exposure variables on the annual changes in log of incidence rates for the pre- and post-periods, respectively. For a continuous outcome  $Y_{ijkt}$ , we will model the mean,  $\mu_{ijkt} = E(Y_{ijkt})$ , with the mixed-effects model and the parameters  $\beta_1$  and  $\beta_2$  indicate the effects of exposure variables on the annual changes in the outcomes for the pre- and post-periods, respectively. All final statistical models will be assessed with respect to the goodness-of-fit and the appropriateness of model assumptions. Statistical software SAS 9.4 and R environment will be used to implement the proposed analyses.

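### Weight loss maintenance, read plainly as a share of the weight lost during counseling, is undefined with no loss, reversed for patients who gained, and has no stable mean

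*Combined protocol and SAP*

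**What the plan says.** Table 1 (Section 7.2) has the same two rows in the pre-diabetes and diabetes blocks. Weight loss during counseling is "Weight lost from first IBT visit to final IBT visit". Weight loss maintenance is a percentage "of weight lost during program and maintained over remaining time period, reported by year".

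No text says who is eligible for the maintenance row, how large a loss must be to count, or what to do with a gain, a zero change or a single IBT visit. Cohort entry does not fill the gap. The at-risk cohort consists of adults "who are at risk for the development of diabetes, based on being overweight", and "Patients will not be removed from the cohort, even if they are no longer overweight". The diabetes cohort is defined by diagnosis and by being captured in the data. The only exclusion in Section 3.2 is "Patients under the age of 18".

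Section 8.0 does not mention maintenance. In general terms it plans medians and quartiles alongside means and SDs as descriptive summaries, mixed-effects models based on "linear regression for a continuous outcome as detailed below", and a check of fit and assumptions for the final models. For the post-policy analysis it uses the number of counseling visits as a predictor.

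**The concern.** A percentage whose base is each patient's own weight loss works when everyone has lost a fair amount. Here the base is an observed change in routine care, so it can be positive, zero or negative, and often small.

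Two things are at stake. First, the score can run against the clinical course: a patient who gained and kept gaining looks like an excellent maintainer. Second, if the row is analysed through its mean, a handful of patients with tiny denominators determine the answer, and the very large sample that the power statement relies on gives no protection.

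The repair an analyst would reach for is to drop everyone who did not lose weight. That would compare patients with few and many visits on differently selected subsets. Aim 1 hypothesizes that more visits bring more loss, so being kept in the analysis would itself depend on the exposure. One-visit patients would disappear altogether.

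**Working it through.** **Inputs.** From Table 1: the program loss runs from first to final IBT visit, and maintenance is a percentage of it in each later year. The plan states no figure for this outcome, so there is none to reproduce. It gives no mean or SD of weight change; those used in steps 3 and 4 are assumptions.

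**Formula on the plain reading.** M = 100 × (W_first − W_year) / (W_first − W_final).

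**Step 1: individual cases (kg; no assumptions needed).**

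| First / final / later | Course | M |
|---|---|---|
| 100 / 95 / 96 | lost 5, holds 4 | 100 × 4/5 = 80% |
| 100 / 100 / 98 | no loss, or one visit only | 2/0, undefined |
| 100 / 102 / 104 | gained, then gained more | 100 × (−4)/(−2) = +200% |
| 100 / 102 / 98 | gained, then fell below start | 100 × 2/(−2) = −100% |
| 100 / 99.9 / 98 | lost 0.1, later 2 below start | 100 × 2/0.1 = +2000% |
| 100 / 99.9 / 102 | lost 0.1, later 2 above start | 100 × (−2)/0.1 = −2000% |

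The first row behaves as intended. Among gainers the better course gets the worse score.

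**Step 2: the mean.** Let L be the program loss and F the later net loss. If L has positive density at zero and F is not forced to zero there, the expected absolute value of M contains an integral of 1/L up to zero, which diverges. Keeping only L > 0 removes one side of that integral and leaves the other, which also diverges. Weights recorded to 0.1 kg cap the ratio, but only at extreme values: a later change of 4 kg over a loss of 0.1 kg is 4000%. A minimum loss well away from zero removes the problem.

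**Step 3: how many patients are affected.** Assume L is normal with mean μ of 1 to 4 kg and SD σ of 4 to 6 kg.

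- P(L ≤ 0) = Φ(−μ/σ). Lowest, μ = 4, σ = 4: Φ(−1) = 0.159. Highest, μ = 1, σ = 6: Φ(−0.167) = 0.434. At μ = 2, σ = 5: Φ(−0.4) = 0.345.
- P(0 < L < 1) = Φ((1 − μ)/σ) − Φ(−μ/σ). Lowest, μ = 4, σ = 6: 0.3085 − 0.2525 = 0.056. Highest, μ = 1, σ = 4: 0.500 − 0.401 = 0.099.

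So about 16 to 43% have no loss, and about 6 to 10% more lost under 1 kg. One-visit patients, whose loss is zero by construction, are not represented in this normal model.

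**Step 4: simulation.** Mean program loss 2, 3 or 5 kg, SD 5 kg; half the loss retained on average, with 4 kg (SD) of later variation; 20 samples of 100,000 patients each.

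- Mean of M: it did not settle. Sample means fell on both sides of zero in every scenario, over all patients and also among losers only, against a built-in 50%. I give no range, because it changes with the random seed.
- Median of M: 49 to 51%, stable. But a gainer who keeps half the gain scores the same 50% as a loser who keeps half the loss.
- Mean of M with a minimum loss of 2 kg (illustrative only): 49 to 51%.
- Mean net change from first visit: 0.98 to 1.03, 1.45 to 1.52 and 2.46 to 2.53 kg, against true values of 1.0, 1.5 and 2.5. Dividing by first-visit weight to give a percentage keeps this stability, since that weight is never near zero.

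**The case against.** The table cell is a loose one-liner. It could mean percent of body weight lost and kept off, which has no near-zero denominator. The outcome's name also suggests that it was meant only for patients who lost something, so that a gainer would simply be not applicable. Both readings are possible, but neither is written down. The second, with any loss above zero admitted, still leaves the mean unstable.

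A reader might infer that the plan commits maintenance to the linear mixed model. It does not say so. Section 8.0 never names the outcome, its example of a continuous outcome is cost, and reporting by year is compatible with description alone. The planned medians are stable. The generic check of model assumptions, and the early extraction used to settle the analysis models, might expose the problem. What remains is that neither supplies a rule for the denominator, so the rule would be chosen after seeing data.

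A reader might also infer that the study's main weight result fails. The documents do not support that. Maintenance is not named as primary, both aims speak of weight loss and diabetes outcomes, and the row for loss during counseling is untouched.

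Finally, net change answers a different question from share retained, and a stated minimum loss also stabilises the ratio. That is correct, though the restricted ratio still describes only patients who succeeded. That success depends on visit count is the study's hypothesis, not an established fact.

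**Conclusion.** The point stands as something that should be fixed, not as a flaw that undermines the study. On the plain reading of Table 1, the undefined values and the reversed sign follow from arithmetic alone. The instability of the mean needs only that program losses can fall near zero. The planned medians avoid the instability but still pool reversed scores.

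If maintenance is modelled where Section 8.0 says "For a continuous outcome" that the mean will be modelled, a few near-zero denominators would drive the estimate. That condition is an inference about how the row will be used. The shares in step 3 rest on an assumed normal distribution of loss, and the size of the problem in this cohort is unknown.

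**What to change.** In both cohort blocks of Table 1, define the analysed maintenance outcome as percent change in weight from the first IBT visit to each later year, for every counseled patient with a weight in that year, whatever happened during counseling. Include first-visit weight as a covariate, and state in Section 8.0 that this outcome goes into the linear mixed model.

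If the share of loss retained is still wanted, report it only as a descriptive secondary measure, by median and quartiles, among patients above a prespecified minimum loss, labelled as conditional on having lost weight. The investigators would need to choose and justify that minimum, and likewise any responder threshold, since the documents give neither.

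The cost is two table rows, a sentence in Section 8.0 and minor programming, using weights already collected. The downside is that the headline measure becomes net change rather than share of loss retained. The change does not give a value to uncounseled patients in the Aim 2 comparison "among those who receive obesity screening and counseling to those who do not"; they have no first IBT visit, and that needs its own rule.

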## 1.0 Objectives

The overarching goal of this proposal is to understand the comparative effectiveness of obesity counseling as covered by Centers for Medicare and Medicaid Services (CMS) in improving weight loss for adults either with or at high risk of type 2 diabetes. CMS and most insurers now include obesity screening and counseling benefits, with no cost sharing to patients. Since overweight patients are at highest risk for diabetes, improved weight management services could prevent diabetes and its negative health outcomes. Beneficiaries with obesity are eligible for up to 20 face-to-face visits for weight counseling in the primary care setting. We propose comparing weight and diabetes outcomes in three states using electronic health record (HER) and claims data before and after this policy was implemented. The PaTH network brings together six academic health systems – the University of Pittsburgh/University of Pittsburgh Medical Center, Penn State College of Medicine/Hershey Medical Center, Temple University School of Medicine/Temple Health, and the Johns Hopkins University/Johns Hopkins Health System/Johns Hopkins Health Care, Geisinger Health Systems, and The University of Utah – to function as an integrated research network and learning health system, providing an infrastructure for observational studies, such as the one proposed here, that require populations beyond a single health system to answer important patient-centered health services questions ([www.pathnetwork.org](http://www.pathnetwork.org)). Using the PaTH Clinical Data Research Network (CDRN) infrastructure, we propose the following specific aims:

**Aim 1: Evaluate the impact of universal preventive service coverage for obesity screening and counseling on weight loss, diabetes incidence, and diabetes outcomes, in patients with diabetes or at high risk for diabetes (defined by body mass index (BMI)  $\geq 25$ ).** We will determine how the annual probability of receiving obesity and/or nutritional counseling (as defined by Current Procedural Terminology (CPT) code) changed pre- and post-policy across all insurers in a cohort of patients with diabetes and at high risk for diabetes. We hypothesize that individual patients are more likely to receive counseling following coverage implementation. Further, we hypothesize that patients who receive a greater number of face-to-face visits will have greater weight loss compared to those who receive fewer visits.

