***Diabetes Cohort Definition.*** During year 1 of the proposed project, the investigative team, in collaboration with the PaTH Network, will identify a valid cohort of patients with type 2 diabetes. The cohort of patients under study will be defined as all patients age 18 and older with an indication of type 2 diabetes during the proposed study time frame. Patients will be classified as having diabetes using a clinically validated algorithm: type 2 diabetes mellitus on the problem list, diabetes-specific medications, hemoglobin A1c (HbA1c) results > 7.0%, or one inpatient diagnosis code or two outpatient diagnosis codes for type 2 diabetes (ICD-9 codes 250.xx). The diabetes cohort will be further limited to patients who will likely be captured in the PaTH EHR records or claims data so that outcome assessments can occur. Thus, we will further limit the diabetes cohort to patients who have either: (1) had at least 2 outpatient primary care visits in one of the PaTH health systems in the past 3 years (since January 1, 2012), or (2) for whom claims data are available. The cohort will be dynamic, with new patients added into the cohort after 2015 as they meet the diabetes cohort definition prospectively. The observational period for the outcome variables will be for the 10-year period from 2009-2019, thus including 3 years of data prior to the first policy change (CMS instituting coverage for intensive behavioral therapy for obesity) and 3 years after the last policy change (Pennsylvania Medicaid expansion) under study.

Following the definition of the diabetes cohort and key diabetes outcomes and covariates as described above, an initial extraction of variables will be conducted in Year 2 of the proposed project for years 2009-2015. This early data extraction from the PaTH Network will allow for cohort validation and data cleaning and editing, as well as required programming and determination of the analysis models. We will utilize this initial data extraction in Years 2 and 3 to analyze the impact of early health policy changes, as well as to prepare a manuscript of both the protocol and early findings of policy impact. The final data extraction will occur during the final quarter of Year 4 of the proposed project, allowing for completion of a ten-year time period (2019).

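### Diabetes incidence is compared by counseling received, but a case can be recorded only through contact with care, which counseling adds; the plan does not separate detection from onset

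*Combined protocol and SAP*

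**What the plan says.** **Outcome.** Table 1 (Section 7.2) defines incidence in the at-risk cohort as the percentage "of patients who develop diabetes per year following weight counseling". The row gives no case definition, no testing requirement and no start of follow-up for patients who were never counseled.

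**Case finding.** The only operational definition of diabetes is in Sections 3.1 and 7.2. Any one of these is enough: "type 2 diabetes mellitus on the problem list, diabetes-specific medications, hemoglobin A1c (HbA1c) results > 7.0" (percent), or "one inpatient diagnosis code or two outpatient diagnosis codes for type 2 diabetes".

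**Exposure.** Section 1.0 states: "Beneficiaries with obesity are eligible for up to 20 face-to-face visits for weight counseling in the primary care setting".

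**Contrasts.** Aim 2 is to "Compare patient weight loss and diabetes-related outcomes among those who receive obesity screening and counseling to those who do not", and it lists diabetes incidence among the outcomes. Section 8.0 enters the number of counseling visits as a predictor in the post-policy models. Aim 1 covers incidence before and after the coverage change.

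**Safeguards.** Cohort members must have "had at least 2 outpatient primary care visits in one of the PaTH health systems in the past 3 years", or simply have claims data. The individual-level covariates in Table 1 are sociodemographics and co-morbidities. A secondary propensity score analysis (Section 8.0) includes use of health care services, with no time window given.

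**The concern.** A problem-list entry, a prescription, a laboratory result and a diagnosis code all arise when a patient is seen or tested. In the Aim 2 models the exposure is a count of visits, and the outcome can be recorded only through contact. A difference in recorded incidence by counseling may therefore reflect onset, detection or both, and the planned analysis cannot tell them apart.

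Detection bias of this kind moves over time. Extra contact first brings forward cases that were present but unrecorded. Once that pool has been drained and the extra contact ends, fewer cases remain to be found. Reported by year, as Table 1 intends, this could look like early harm followed by later protection. With about two million at-risk patients, a difference due to detection alone could easily reach statistical significance.

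**Working it through.** **1. The plan's own figures.** The plan gives no incidence, testing rate, counseling uptake or numeric power to reproduce. The site totals for the at-risk cohort in Section 7.2 do add up: 167,799 + 950,020 + 471,860 + 212,314 + 260,506 = 2,062,499.

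**2. Testing-share model.** The inputs are assumptions, not from the documents: the same rare, constant onset in both groups (1 unit per year); testing independent from year to year; share tested 50% without and 85% with counseling; both groups at steady state at 50% beforehand.

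Each year, pool = last year's undetected cases + 1; detected = share × pool; carried over = (1 − share) × pool.

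- Steady state at 50%: pool = 1/0.50 = 2.00, detected = 1.00 per year. This is the uncounseled group throughout.
- Counseled, year 1: 0.85 × 2.00 = 1.70; carried over 0.30.
- Year 2, testing stays at 85%: 0.85 × 1.30 = 1.105.
- Year 2, testing reverts to 50%: 0.50 × 1.30 = 0.65.

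| Ratio, counseled vs not | Yr 1 | Yr 2 | Yr 3 | Yr 4 | Yr 5 | Yr 6 | Six years |
|---|---|---|---|---|---|---|---|
| Testing stays at 85% | 1.70 | 1.105 | 1.02 | 1.00 | 1.00 | 1.00 | 6.82/6 = 1.14 |
| Testing reverts after year 1 | 1.70 | 0.65 | 0.83 | 0.91 | 0.96 | 0.98 | 6.02/6 = 1.00 |

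With sustained shares of 60% vs 80%, the year-1 ratio is 0.80/0.60 = 1.33 and the six-year ratio 1.07. With 40% vs 90% they are 0.90/0.40 = 2.25 and 1.23.

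**3. Visit-based model.** This has three states (healthy, undiagnosed, diagnosed), with detection rate = visits per year × chance of detection per visit. Assumed: onset 1% to 2% a year in both groups, 0.67 to 2 usual visits a year, chance 0.10 to 0.50 per visit, and 2 to 20 extra visits, all in year 1.

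- Year-1 ratio 1.43 to 13.8. At onset 2%, 2 usual visits, chance 0.25 and 20 extra visits, recorded incidence is 1.97% vs 5.51%, ratio 2.80.
- Year-2 ratio 0.13 to 0.86.
- Six-year cumulative ratio 1.00 to 2.38.
- If the extra visits bring no tests or codes, the ratio is 1.00.
- Chance that a two-sided 0.05 test calls the false year-1 difference significant among 2,062,499 patients: about 1.00 if 1% are counseled, 0.50 to 1.00 if 0.1%.

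**4. Pre/post-policy contrast.** If a share s is counseled, the whole-population year-1 ratio is 1 + s × (R − 1), where R is the counseled-group ratio. With R = 2.80 and s = 1%: 1 + 0.01 × 1.80 = 1.018. Across three scenarios (R = 1.43, 2.80 and 13.80) it is 1.0004 to 1.013 at 0.1% uptake, 1.004 to 1.13 at 1%, and 1.02 to 1.64 at 5%.

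**5. Restricting to tested person-years.** In the model of step 2 with testing kept at 85%, yield per tested uncounseled person is 1.00/0.50 = 2.00 every year. For counseled persons it is 1.70/0.85 = 2.00 in year 1 and 1.105/0.85 = 1.30 in year 2, and it settles at 1/0.85 = 1.18. The ratios are 1.00, 0.65 and then 0.59, an apparent benefit with identical onset.

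**The case against.** A reader might infer that counseled and post-policy patients will necessarily be found diabetic more often, by a lasting factor such as 1.7. The documents do not support this, on four counts.

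- **Mechanism.** Nothing says that counseling visits carry HbA1c or glucose tests or diabetes codes. The bias is conditional on that.
- **Persistence.** A ratio of 1.70 in every year would require the same people to go untested year after year. Otherwise the excess fades, and it reverses if testing drops back. Section 8.0 models several post-policy years, so a first-year figure is not the result.
- **Reach.** The 20 visits are a ceiling for patients with obesity, while the cohort starts at BMI 25. By the Section 7.2 totals, (592,741 + 312,277 + 211,363)/2,062,499 = 54% have BMI 30 or more. Uptake is not given, and at low uptake the policy contrast barely moves.
- **The two-code rule.** It is tempting to size the problem on this rule alone, but the routes are alternatives. A patient short of two codes may qualify by problem list, drug, HbA1c or inpatient code.

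The plan also has partial safeguards in the two-visit filter and the propensity score on use of care. They do not settle the matter. The filter sets a floor, with no minimum for patients who enter through claims. Use of care before counseling cannot remove contact that counseling creates, and use of care after it starts is a consequence of exposure. Finally, Table 1 does not say that incidence uses the Section 7.2 algorithm. That is an inference, and the missing definition is itself a gap to close.

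**Conclusion.** The concern holds as a conditional risk. The contrasts by counseling status and by number of counseling visits can show a difference in recorded incidence with no difference in onset, and the main models do nothing to separate the two. On the assumed shares the false ratio is 1.70 in year 1, about 1.0 by years 3 to 4 and 1.14 over six years, or 0.65 in year 2 and 1.00 over six years if testing reverts. All of these sizes rest on assumed testing or detection rates that the documents do not give.

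Yearly rates are the most exposed. Cumulative incidence is less so, though not immune where baseline detection is low (up to 2.38 in the visit-based model). The pre/post-policy contrast is affected only as far as counseling uptake is material. A reader might also infer that tested person-years should become the main analysis. Step 5 of the working shows that this can produce false protection, so it belongs among the sensitivity analyses.

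**What to change.** Keep all person-years as the main incidence analysis, and add to the SAP:

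1. The rule for an incident case, and a start date for uncounseled patients comparable with the start of counseling.
2. HbA1c testing rates and non-counseling visit rates, by counseling group and year, shown beside the incidence result.
3. Multi-year cumulative incidence beside the yearly rates.
4. Sensitivity analysis (a): codes recorded at counseling visits do not count toward the two-code rule.
5. Sensitivity analysis (b): person-years with an HbA1c result, with inverse-probability-of-testing weights whose model includes counseling, and a note that this analysis can show false protection in later years.
6. A statement that a preventive or harmful conclusion will be drawn only if it is consistent across these analyses.

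The cost is SAP wording and modest extra analysis, provided that the extract holds dated HbA1c results and identifies counseling visits, as the case algorithm and the exposure definition already require. Analysis (a) may under-count some cases in the counseled group. Analysis (b) loses person-years and rests on the testing model.
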